#### **7.5.2.7 Post-Study Adverse Events**

The investigator should expeditiously report any SAE occurring after a subject has completed or discontinued study participation if attributed to prior atezolizumab exposure. If the investigator should become aware of the development of cancer or a congenital anomaly in a subsequently conceived offspring of a female subject who participated in the study, this should be reported as an SAE.

#### **7.5.2.8 Reconciliation (Case Transmission Verification)**

The Investigator agrees to conduct reconciliation for the product. Genentech and the Investigator will agree to the reconciliation periodicity and format, but agree at minimum to exchange quarterly line listings of cases received by the other party.

If discrepancies are identified, the Investigator and Genentech will cooperate in resolving the discrepancies. The responsible individuals for each party shall handle the matter on a case-by-case basis until satisfactory resolution. The Investigator shall receive reconciliation guidance documents within the 'Activation Package'.

Following Case Transmission Verification, single case reports which have not been received by Genentech shall be forwarded by the Investigator to Genentech within five (5) calendar days from request by Genentech.

At the end of the study, a final cumulative Case Transmission Verification (CTV) report will be sent to Genentech.

### **7.6 Adverse Event Reporting**

The Investigator will be responsible for collecting all protocol-defined Adverse Events (AEs)/Serious Adverse Events (SAEs), AEs of Special Interest (AESIs), Special Situation Reports (including pregnancy reports) and Product Complaints (with or without an AE) originating from the Study for the Product.

Investigators must report all the above-mentioned single case reports adequately to Genentech within the timelines described below. The completed MedWatch or CIOMS I form, or Genentech approved reporting forms should be faxed/mailed immediately upon completion to Genentech at the following contacts:

All protocol-defined AEs, SAEs, AESIs, Special Situation Reports (including pregnancy reports) and Product Complaints with an AE should be sent to:

[contact]

Email: [usds\\[contact]](mailto:[contact])

Batch ID/lot ID for biologics associated with AE/SSR/PC/AESI must be included when submitting the case reports to Genentech.

All Product Complaints without an AE should call via:

PC [contact] (M-F: 5 am to 5 pm PST)

Transmission of these reports (initial and follow-up) will be either electronically or by fax and within the timelines specified below:

Type of Report	Timelines
Serious Adverse Events (related and not related to the Product)	
Special Situation Reports ( With or without AE and pregnancy)	30 calendar days from awareness date
Product Complaints (With or without AE)	
AESI	

It is understood and agreed that the Sponsor will be responsible for the evaluation of AEs, SAEs, AESIs, Special Situation reports (including pregnancy reports) and Product Complaints (with or without an AE) originating from the study.

### **Other Special Situation Reports**

In addition to all SAEs, pregnancy reports and AESIs, the following other Special Situations Reports should be collected and transmitted to Genentech even in the absence of an Adverse Event within thirty (30) calendar days:

- Data related to product usage during breastfeeding
- Data related to overdose, abuse, misuse or medication error (including potentially exposed or intercepted medication errors)
- In addition, reasonable attempts should be made to obtain and submit the age or age group of the patient, in order to be able to identify potential safety signals specific to a particular population

### **Product Complaints**

All Product Complaints (with or without an AE) shall be forwarded to Genentech within thirty (30) calendar days of the awareness date.

- A Product Complaint is defined as any written or oral information received from a complainant that alleges deficiencies related to identity, quality, safety, strength, purity, reliability, durability, effectiveness, or performance of a product after it has been released and distributed to the commercial market or clinical trial.

#### **7.6.1 MedWatch 3500A Reporting Guidelines**

In addition to completing appropriate patient demographic (Section A) and suspect medication information (Section C and D), the report should include the following information within the Event Description (Section B.5) of the MedWatch 3500A form:

- Protocol number and title description
- Description of event, severity, treatment, and outcome if known
- Supportive laboratory results and diagnostics (Section B.6)
- Investigator's assessment of the relationship of the adverse event to each investigational product and suspect medication

#### **7.6.1.1 Follow-up Information**

Additional information may be added to a previously submitted report by any of the

following methods:

- Adding to the original MedWatch 3500A report and submitting it as follow-up
- Adding supplemental summary information and submitting it as follow-up with the original MedWatch 3500A form
- Summarizing new information and faxing it with a cover letter including patient identifiers (i.e., D.O.B. initial, patient number), protocol description and number, if assigned, brief adverse event description, and notation that additional or follow-up information is being submitted (The patient identifiers are important so that the new information is added to the correct initial report)

MedWatch 3500A (Mandatory Reporting) form is available at

<https://www.fda.gov/media/69876/download>

### **7.6.2 Reporting to Regulatory Authorities, Ethics Committees and Investigators**

Genentech, as the Marketing Authorization Holder, will be responsible for the reporting of individual case safety reports from the study to the regulatory authority in compliance with applicable regulations.

The Investigator, as the Sponsor of the Study, will be responsible for the expedited reporting of safety reports originating from the Study to the Regulatory Authorities (FDA) where it has filed a clinical trial approval, in compliance with local regulations.

The Investigator, as the Sponsor of the Study, will be responsible for the expedited reporting of safety reports originating from the Study to the EMA through Eudravigilance Clinical Trial Module (EVCTM), where applicable.

The Investigator will be responsible for the expedited reporting of safety reports originating from the Study to the Ethics Committees and Institutional Review Boards (IRB), where applicable.

Genentech will be responsible for the distribution of safety information to its own investigators, where relevant, in accordance with local regulations.

## **7.7 Aggregate Reports**

### **7.7.1 Development Safety Update Report**

The Parties agree that aggregate reporting obligations for the Study (including Development

Safety Update Report [DSURs] and/or Investigational New Drug [IND]) Annual Reports) in accordance to the applicable laws and regulations in the concerned countries will reside with the investigator, as the Sponsor of the Study.

Upon request, the investigator agrees to share a copy of their own DSUR with Genentech as soon as reasonably possible after completion.

Genentech will forward to the investigator an executive summary of the Genentech DSUR upon request. Furthermore, Genentech agrees that the investigator may cross-reference the executive summary of the Genentech DSUR, as applicable.

### **7.7.2 Other Reports**

The Investigator will forward a copy of the Publication to Genentech upon completion of the Study.

## **7.8 Study Close-Out**

Any study report submitted to the FDA by the Sponsor-Investigator should be copied to Genentech. This includes all IND annual reports and the Clinical Study Report (final study report). Additionally, any literature articles that are a result of the study should be sent to Genentech. Copies of such reports should be mailed to the assigned Clinical Operations contact for the study:

Atezolizumab IIS Clinical Operations: [[contact]](mailto:[contact])

And to Genentech Drug Safety CTV oversight mail box at: [[contact]](mailto:[contact])

## **Queries**

Queries related to the Study will be answered by the Investigator. However, responses to all safety queries from regulatory authorities or for publications will be discussed and coordinated between the Parties. The Parties agree that Genentech shall have the final say and control over safety queries relating to the Product. The Investigator agrees that it shall not answer such queries from regulatory authorities and other sources relating to the Product independently but shall redirect such queries to Genentech.

Both Parties will use all reasonable effort to ensure that deadlines for responses to urgent requests for information or review of data are met. The Parties will clearly indicate on the request the reason for urgency and the date by which a response is required.

## **Signal Management and Risk Management**

Genentech is responsible for safety signal management (signal detection and/or evaluation) for their own Product. However, it is agreed that investigator, as Sponsor of the Study, will be primarily responsible for assessment of the benefit-risk balance of the Study.

If investigator - sponsor, issues a safety communication relevant for Genentech (i.e., a safety issue that notably impacts the benefit-risk balance of the Study and / or triggers any changes to the Study) this will be sent to Roche within five (5) business days of its

internal approval.

As needed, Genentech will reasonably assist investigator - sponsor with signal and risk management activities related to the Product within the Study.

Genentech will also provide investigator - sponsor with any new relevant information that may modify or supplement known data regarding the Product (e.g., relevant Dear Investigator Letter).

### **Compliance with Pharmacovigilance Agreement / Audit**

The Parties shall follow their own procedures for adherence to AE reporting timelines. Each Party shall monitor and, as applicable, request feedback from the other Party regarding AE report timeliness in accordance with its own procedures. The Parties agree to provide written responses in a timely manner to inquiries from the other Party regarding AE reports received outside the agreed upon Agreement timelines. If there is any detection of trends of increasing or persistent non-compliance to transmission timelines stipulated in this Agreement, both Parties agree to conduct ad hoc or institute a regular joint meeting to address the issue. In case of concerns related to non-compliance of processes, other than exchange timelines, with this Agreement, the Parties will jointly discuss and collaborate on clarifying and resolving the issues causing non-compliance. Every effort will be made by the non-compliant Party to solve the non-compliance issues and inform the other Party of the corrective and preventative actions taken.

Upon justified request, given sufficient notice of no less than sixty (60) calendar days, an audit under the provisions of this Agreement can be requested by either Party. The Parties will then discuss and agree in good faith upon the audit scope, agenda and execution of the audit. The requesting Party will bear the cost of the audit.

## **8. CORRELATIVE/SPECIAL STUDIES**

### Blood collection methods:

Up to 150 ml of blood may be taken for research at baseline, after the first cycle of therapy, and at surgery for a maximum total of 300 ml of blood for research purposes within the period of a month. The blood will be drawn in Vacutainer tubes. These tubes, barcoded labels, and a transport envelope will be provided by the study coordinator(s). The blood will be drawn by a phlebotomist or appropriately qualified person. The tubes will be labeled with the barcode labels placed in an envelope (which will be included with the tubes) and kept at room temperature. A barcode label will also be placed on an intake form that has the patient study ID number. The study coordinator will then be notified of the blood samples and will arrange for transport to the Biobank section of the CTRU.

We will be collecting plasma, serum, and PMBCs from the blood which will be used for the following:

- Plasma samples for exploratory assessment cell-free DNA at baseline, after the first cycle of therapy, and at surgery.

- Serum samples for assessment of cytokine profiles associated with immune system activation.
- Peripheral blood mononuclear cells (PBMC) will be collected and cryopreserved at baseline, after the first cycle of therapy, and at surgery if deemed for possible, for exploratory identification of antigen-specific T cell receptors (TCR).

Tumor sampling methods:

When each patient is enrolled on this study, he or she will be assigned an anonymized bar code for all samples. The study coordinator will link the barcodes to the patient. The key will be kept in REDCap. If archival tissue is unavailable at the time that the patient signs consent, or is deemed unsuitable for exploratory research, a pretreatment biopsy is required. Tumor tissue sample will also be obtained following the first cycle of therapy and at the time of surgical resection, if deemed clinically feasible, for exploratory research on biomarkers. The least invasive technique to obtain the sample will be used. Samples collected via resection, core-needle biopsy, or excisional, incisional, punch, or forceps biopsy are preferred. However, all specimen types (e.g., fine-needle aspiration) are acceptable. If the tissue collected is fresh, the tissue will be placed in saline on ice, and [name] laboratory personnel will be notified.

The exploratory biomarker research may include, but will not be limited to analysis of genes or gene signatures associated with tumor immunobiology, PD-L1, lymphocyte subpopulations, T-cell receptor repertoire, peptide-MHC repertoire, or cytokines associated with T-cell activation. Research may involve extraction of DNA, circulating tumor DNA, or RNA, analysis of mutations, genomic profiling through use of next-generation sequencing (NGS) of a comprehensive panel of genes, and analysis of proteins. Research will aim to distinguish germline mutations from somatic mutations and understanding mechanisms underlying immune cell recognition of tumor cells that might predict clinical response to therapy. NGS methods may include whole exome sequencing (WES). De-identified biospecimen may be sent to other (external) collaborators.

Please refer to section 4.6 for further information.

## 9. STUDY CALENDAR

	Screening a	Treatment Cycles (21-day cycles)					Surgery	Follow-Up (or Treatment Discontinuation b )
		Cycle 1		Cycle 2		Cycle 3		
	Within 28 days prior to start of treatment	Day 1 (± 3 days)	Day 14 (± 7 days)	Day 21 (± 3 days)	Day 38 (± 4 days)	Day 42 (± 3 days)	2-4 weeks after Cycle 3	10 days ± 5 days after surgery (or < 30 days after last treatment)
Informed consent	X c							
Baseline tumor tissue sample d	X							
Second tumor tissue sample, if clinically feasible			X					
Demographic data	X							
Medical history and baseline conditions	X							
Vital signs e	X	X		X		X		X
Weight	X	X		X		X		X
Height	X							
Complete physical examination f	X							X
Limited physical examination g		X		X		X		
Digital Photography	X		X				X	
ECOG Performance Status	X							X
ECG h	X							
Hematology i	X j	X k		X		X		X

	Screening a	Treatment Cycles (21-day cycles)					Surgery	Follow-Up (or Treatment Discontinuation b )
		Cycle 1		Cycle 2		Cycle 3		
	Within 28 days prior to start of treatment	Day 1 (± 3 days)	Day 14 (± 7 days)	Day 21 (± 3 days)	Day 38 (± 4 days)	Day 42 (± 3 days)	2-4 weeks after Cycle 3	10 days ± 5 days after surgery (or < 30 days after last treatment)
Chemistry l	x j	x k		x		x		x
Pregnancy test m	x j							
Coagulation (INR, aPTT)	x j							
TSH n	x j							x
Urinalysis o	x j							
CT or MRI of primary site (if present) and regional lymphatics	x p				x p (prior to cycle 3)			
Chest CT with contrast or PET scan	x p							
Blood sample for exploratory biomarker research q	x		x				x	
Tumor response assessments s	x r	x s		x		x	x	
Concomitant medications t	x	x		x		x		x
Adverse events u	x u	x u		x u		x u		x u
Atezolizumab administration v		x		x		x		
Surgical resection							SOC	
Adjuvant Therapy w								SOC

	Screening a	Treatment Cycles (21-day cycles)					Surgery	Follow-Up (or Treatment Discontinuation b )
		Cycle 1		Cycle 2		Cycle 3		
	Within 28 days prior to start of treatment	Day 1 ( $\pm$ 3 days)	Day 14 ( $\pm$ 7 days)	Day 21 ( $\pm$ 3 days)	Day 38 ( $\pm$ 4 days)	Day 42 ( $\pm$ 3 days)	2-4 weeks after Cycle 3	10 days $\pm$ 5 days after surgery (or < 30 days after last treatment)

ADA=anti-drug antibody; HBcAb=hepatitis B core antibody; HBsAb=hepatitis B surface antibody; HBsAg=hepatitis B surface antigen; NA=not applicable; PK=pharmacokinetic; T3=triiodothyronine; T4=thyroxine; TSH=thyroid-stimulating hormone; WES=whole exome sequencing; WGS=whole genome sequencing.

Notes: On treatment days, all assessments should be performed prior to dosing, unless otherwise specified.

Assessments shaded in gray should be performed as scheduled, but the associated data do not need to be recorded in the patient's medical records (except in the case of an adverse event).

- a Results of standard-of-care tests or examinations performed prior to obtaining informed consent and within 28 days prior to start of treatment may be used; such tests do not need to be repeated for screening.
- b Patients who discontinue study treatment will return to the clinic for a treatment discontinuation visit not more than 30 days after the last dose of study treatment. The visit at which response assessment shows progressive disease may be used as the treatment discontinuation visit.
- c Informed consent must be documented before any study-specific screening procedure is performed, and may be obtained more than 28 days before initiation of study treatment.
- d If archival tissue is unavailable or is determined to be unsuitable for required testing, a pretreatment tumor biopsy is required. A pretreatment tumor biopsy will also be performed, when clinically feasible, for biomarker assessment. Refer to Section 4.6 or tissue sample requirements.
- e Includes respiratory rate, pulse rate, and systolic and diastolic blood pressure, and temperature. Record abnormalities observed at baseline in the patient's medical records. At subsequent visits, record new or worsened clinically significant abnormalities in the patient's medical records. For the first and subsequent infusions, vital signs should be measured prior to the infusion (taken same day during clinic visit or in infusion area) and, if clinically indicated, during or after the infusion.
- f Record abnormalities observed at baseline in the patient's medical records. At subsequent visits, record new or worsened clinically significant abnormalities in the patient's medical records.
- g Perform a limited, symptom-directed examination at specified timepoints and as clinically indicated at other timepoints. Record new or worsened clinically significant abnormalities in the patient's medical records.

---

- h ECG recordings will be obtained during screening and as clinically indicated at other timepoints.
- i Hematology includes WBC count, hemoglobin, hematocrit, platelet count, differential count.
- j Screening laboratory test results must be obtained within 28 days prior to initiation of study treatment.
- k If screening laboratory assessments were performed within 96 hours prior to Day 1 of Cycle 1, they do not have to be repeated.
- l Chemistry panel (serum or plasma) includes sodium, potassium, chloride, bicarbonate, glucose, BUN or urea, creatinine, total protein, albumin, calcium, total bilirubin, alkaline phosphatase, ALT, AST.
- m All women of childbearing potential will have a serum pregnancy test at screening, within 28 days prior to initiation of study treatment.
- n Past TSH lab value may be used for screening if collected within 6 weeks prior to the first administration of atezolizumab.
- o Urinalysis includes pH, specific gravity, glucose, protein, ketones, and blood
- p Baseline imaging with CT or MRI of primary site (if present) and regional lymphatics; CT Chest or PET scan will be performed only if scans were not previously performed within 28 days of screening assessment. The same radiographic modality used to assess disease sites at screening should be used for subsequent tumor assessment at baseline and after cycle 2. **RECIST measurements are only required at baseline, after cycle 2, and ORR can be assessed after cycle 2/surgery.**
- q See Section 4.6 for details on exploratory research
- r All measurable and evaluable lesions should be assessed and documented at screening. Tumor assessments performed as standard of care prior to obtaining informed consent and within 28 days prior to initiation of study treatment do not have to be repeated at screening.
- s Patients will undergo clinical tumor assessments at baseline and once per cycle. All measurable and evaluable lesions should be re-assessed at each subsequent tumor evaluation. **RECIST measurements are only required at baseline, after cycle 2, and ORR can be assessed after cycle 2/surgery.**
- t Medication (e.g., prescription drugs, over-the-counter drugs, vaccines, herbal or homeopathic remedies, nutritional supplements) used by a patient in addition to protocol-mandated treatment from 7 days prior to initiation of study treatment until the treatment discontinuation visit.
- u After informed consent has been obtained but prior to initiation of study treatment, only serious adverse events caused by a protocol-mandated intervention should be reported. After initiation of study treatment, all adverse events will be reported until 30 days after the last dose of study treatment or until initiation of new systemic anti-cancer therapy, whichever occurs first, and serious adverse events and adverse events of special interest will continue to be reported until 90 days after the last dose of study treatment or until initiation of new systemic anti-cancer therapy, whichever occurs first. After this period, all deaths, regardless of cause, should be reported. In addition, Genentech, Inc. should be notified if the investigator becomes aware of any serious adverse event that is believed to be related to prior exposure to study treatment (see Section 5.6). The investigator should follow each adverse event until the event has resolved to baseline grade or better, the event is assessed as stable by the investigator, the patient is lost to follow-up, or the patient withdraws consent. Every effort should be made to follow all serious adverse events considered to be related to study treatment or trial-related procedures until a final outcome can be reported.

	Screening a	Treatment Cycles (21-day cycles)					Surgery	Follow-Up (or Treatment Discontinuation b )
		Cycle 1		Cycle 2		Cycle 3		
	Within 28 days prior to start of treatment	Day 1 ( $\pm$ 3 days)	Day 14 ( $\pm$ 7 days)	Day 21 ( $\pm$ 3 days)	Day 38 ( $\pm$ 4 days)	Day 42 ( $\pm$ 3 days)	2-4 weeks after Cycle 3	10 days $\pm$ 5 days after surgery (or < 30 days after last treatment)

- v The initial dose of atezolizumab will be delivered over 60 ( $\pm$  15) minutes. Subsequent infusions will be delivered over 30 ( $\pm$  10) minutes if the previous infusion was tolerated without infusion-associated adverse events, or 60 ( $\pm$  15) minutes if the patient experienced an infusion-associated adverse event with the previous infusion.
- w Adjuvant therapy will be delivered as per standard of care for head and neck cutaneous squamous cell carcinoma. AJCC Stage 3 and 4 lesions will receive adjuvant radiation therapy beginning 4-8 weeks after the completion of surgery unless the patient is deemed medically unfit, or patient declines further treatment.

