## **4. TREATMENT PLAN**

### **Description of the Study**

The schedule of activities to be performed during the study is provided in Section 9. All activities must be performed and documented for each patient. Patients will be closely monitored for safety and tolerability throughout the study. Patients should be assessed for toxicity prior to each dose; dosing will occur only if the clinical assessment and local laboratory test values are acceptable.

Atezolizumab will be administered at a fixed dose of 1200 mg Q3W (1200 mg on Day 1 (+/- 3 days) of each 21-day cycle), which is the approved dosage for atezolizumab, as outlined in the prescribing information. Anti-tumor activity has been observed across doses ranging from 1 mg/kg to 20 mg/kg Q3W. In Study PCD4989g, the maximum tolerated dose of atezolizumab was not reached and no DLTs were observed at any dose. The fixed dose of 1200 mg Q3W (equivalent to an average body weight-based dose of 15 mg/kg Q3W) was selected on the basis of both nonclinical studies (Deng et al. 2016) and available clinical pharmacokinetic, efficacy, and safety data (refer to the Atezolizumab Investigator's Brochure for details).

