#### **4.6    Laboratory, Biomarker, and other Biological Samples**

Samples for the following laboratory tests will be sent to the study site's local laboratory for analysis:

- See study calendar (Section 9) for details about schedule of laboratory studies

The following samples will be sent to the Investigator or a designee for analysis:

- Plasma samples for exploratory assessment cell-free DNA at baseline and after each cycle of therapy (up to 3 cycles).
- Serum samples for assessment of cytokine profiles associated with immune system activation.
- Peripheral blood mononuclear cells (PBMC) will be collected and cryopreserved after each cycle of therapy (up to 3 cycles) and at the time of surgical resection if deemed for possible, for exploratory identification of antigen-specific T cell receptors (TCR).
- Archival or newly collected tumor tissue sample obtained at baseline for exploratory research on biomarkers
  - Samples collected via resection, core-needle biopsy, or excisional, incisional, punch, or forceps biopsy are preferred. However, all specimen types (e.g., fine-needle aspiration) are acceptable.
  - If archival tumor tissue is unavailable or is determined to be unsuitable for exploratory research, a pretreatment tumor biopsy is required.

- Tumor tissue sample obtained following the first and subsequent cycles of therapy and at the time of surgical resection, if deemed clinically feasible, for exploratory research on biomarkers
  - Samples collected via resection, core-needle biopsy (at least three cores preferred), or excisional, incisional, punch, or forceps biopsy are preferred.

Exploratory biomarker research may include, but will not be limited to, analysis of genes or gene signatures associated with tumor immunobiology, PD-L1, lymphocyte subpopulations, T-cell receptor repertoire, peptide-MHC repertoire, or cytokines associated with T-cell activation. Research may involve extraction of DNA, circulating tumor DNA, or RNA, analysis of mutations, genomic profiling through use of next-generation sequencing (NGS) of a comprehensive panel of genes, and analysis of proteins. Research will aim to distinguish germline mutations from somatic mutations and understanding mechanisms underlying immune cell recognition of tumor cells that might predict clinical response to therapy. NGS methods may include whole exome sequencing (WES).

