### **7.1 Potential Adverse Events**

Atezolizumab has been associated with risks such as the following: IRRs and immune-related hepatitis, pneumonitis, colitis, pancreatitis, diabetes mellitus, hypothyroidism, hyperthyroidism, adrenal insufficiency, hypophysitis, Guillain-Barré syndrome, myasthenic syndrome or myasthenia gravis, meningoencephalitis, myocarditis, nephritis, and myositis. Immune-mediated reactions may involve any organ system and may lead

to hemophagocytic lymphohistiocytosis and macrophage activation syndrome. Refer to Appendix 9 of the protocol and Section 6 of the Atezolizumab Investigator's Brochure for a detailed description of anticipated safety risks for atezolizumab.

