#### IV. Inclusion/Exclusion Criteria

Inclusion/Exclusion Criteria			
Inclusion Criteria (From IRB approved protocol)	Yes	No	Supporting Documentation*
1. Signed Informed Consent Form			
2. Age $\geq$ 18 years at time of signing Informed Consent Form			
3. Histologically or cytologically confirmed squamous cell carcinoma			
4. Measurable disease per RECIST v1.1 

• Note that protocol specified imaging is not necessary to fulfill this criterion. For example, a patient presenting with a visible 4cm primary lesion who has obviously RECIST evaluable disease may be considered eligible prior to baseline imaging stipulated in the protocol.

			
5. Availability of a representative tumor specimen that is suitable for determination of PD-L1 immunohistochemical stain evaluation.			
6. ECOG Performance Status of 0 or 1			

Inclusion/Exclusion Criteria			
Inclusion Criteria (From IRB approved protocol)	Yes	No	Supporting Documentation*
7. Adequate hematologic and end-organ function appropriate for surgery as determined by routine preoperative evaluation. If liver function, renal function and hematologic laboratory test results are within limits acceptable for elective surgery. Laboratory results that will need to be obtained within 28 days prior to initiation of study treatment: 
 
AST, ALT, total bilirubin, and alkaline phosphatase (ALP) ≤ 2.5 x upper limit of normal (ULN.).
 
TSH < 13 
 
Patients with a history of a high TSH who are receiving levothyroxine replacement at the time of eligibility evaluation and have no clinical evidence of hypothyroidism are eligible.
 
 
 
			
8. For patients receiving therapeutic anticoagulation: stable anticoagulant regimen			
9. Negative hepatitis B surface antigen (HBsAg) test at screening			

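### For patients who complete treatment, the calendar schedules TSH only at Screening and after surgery, so a symptom-free thyroid change has no scheduled test before dose 2, dose 3 or surgery (minor; cheap to improve)

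*Combined protocol and SAP*

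**What the plan says.** In the Section 9 calendar, the TSH row has two marks, one at Screening and one in the last column (Follow-Up or Treatment Discontinuation), timed "10 days ± 5 days after surgery (or < 30 days after last treatment". Footnote b assigns the under-30-day alternative to patients who discontinue study treatment. A completer is therefore tested 5 to 15 days after surgery.

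Hematology and chemistry are marked in five columns: Screening, Cycle 1 Day 1, Day 21, Day 42 and Follow-Up. Footnote l defines the panel ("Chemistry panel (serum or plasma) includes sodium, potassium, chloride, bicarbonate, glucose", and so on) and lists no thyroid test. Section 4.6 gives no separate laboratory schedule: "See study calendar (Section 9) for details about schedule of laboratory studies".

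Three other parts of the protocol bear on thyroid function:

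- Section 7.1 names "diabetes mellitus, hypothyroidism, hyperthyroidism, adrenal insufficiency, hypophysitis" among the drug's risks.
- Section 4 (Description of the Study) says that "dosing will occur only if the clinical assessment and local laboratory test values are acceptable", without naming the tests.
- Appendix I, Table 4, starts thyroid replacement at Grade 1 hypothyroidism. It splits Grade 1 hyperthyroidism at a TSH of 0.1 mU/L and sends the lower band to the Grade 2 guidance, under which a hold is optional.

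On the age of the entry test, footnote j says "Screening laboratory test results must be obtained within 28 days prior to initiation of study treatment" and inclusion criterion 7 agrees ("Laboratory results that will need to be obtained within 28 days prior to initiation of study treatment"). Footnote n allows a TSH up to six weeks old.

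**The concern.** The protocol treats thyroid disease as a known effect of the drug and has management rules that use a TSH value. For a completer without symptoms, however, nothing on the calendar supplies that value between the first dose and surgery.

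Three things follow. A silent change cannot be dated relative to the doses from scheduled tests. A change that resolves before Follow-Up is not seen by them. And the latest scheduled TSH at surgery always predates the drug. An earlier value could prompt replacement, or an optional hold, before the operation. Safety and tolerability is a secondary objective in Section 1.2, so the schedule also limits what the trial can say about the timing of thyroid effects.

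**Working it through.** The plan states no figure for this interval, so there is none to reproduce. The intervals follow from the visit windows.

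**Inputs (Section 9 calendar and footnotes)**

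- Dose 1 is taken as Day 1.
- Dose 2 is at Day 21 ± 3, so Day 18 to 24. Dose 3 is at Day 42 ± 3, so Day 39 to 45.
- Surgery is 14 to 28 days after Cycle 3, counted here from dose 3.
- Follow-Up is 5 to 15 days after surgery.
- The screening TSH is 0 to 28 days before dose 1 (footnote j, criterion 7), or up to 42 days (footnote n).
- The patient completes on schedule with no held dose.

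**Present schedule**

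- Surgery: Day 39 + 14 = 53 to Day 45 + 28 = 73.
- Follow-Up TSH: Day 53 + 5 = 58 to Day 73 + 15 = 88.
- Follow-Up TSH after dose 3: 14 + 5 = 19 to 28 + 15 = 43 days.
- Follow-Up TSH after dose 1: 58 − 1 = 57 to 88 − 1 = 87 days.
- Gap between the two scheduled tests: 57 to 87 + 28 = 115 days, or up to 87 + 42 = 129 under footnote n.
- Age of the latest scheduled TSH at surgery: 53 − 1 = 52 to (73 − 1) + 28 = 100 days, or up to 72 + 42 = 114 under footnote n.

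**With TSH added at Day 21 and Day 42**

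The calendar notes say "On treatment days, all assessments should be performed prior to dosing, unless otherwise specified", so each sample precedes that day's dose.

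- Dose 1 to the Day 21 sample: 18 − 1 = 17 to 24 − 1 = 23 days.
- Day 21 to Day 42 sample: 39 − 24 = 15 to 45 − 18 = 27 days.
- Day 42 sample to Follow-Up: 19 to 43 days.

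| Quantity (days) | Now | With the two added tests |
|---|---|---|
| Dose 1 to first scheduled TSH | 57 to 87 | 17 to 23 |
| Longest stretch after dose 1 without one | up to 87 | up to 43 |
| Age of latest TSH at surgery | 52 to 100 (114) | 14 to 28 |

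The figure in parentheses uses the six-week allowance.

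**Sensitivity**

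- If surgery is counted from the end of the 21-day third cycle, add 21 days. The first post-dose TSH is then 78 to 108 days after dose 1. The age at surgery is 73 to 121 days (135 with footnote n), and the gap between tests is 78 to 136 (150). With the added tests, the longest stretch is 64 days and the age at surgery is 35 to 49.
- If the ± 3-day window is applied to dose 1 as well, 57 to 87 becomes 54 to 90.
- Appendix I allows holds of up to 12 weeks, and longer in some cases. A held dose takes a patient outside all these ranges.

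**The case against.** The strongest reply is that this is a choice about monitoring and not an error. No section requires a TSH at each cycle, and no mandatory hold in Table 4 rests on a TSH value alone. Symptomatic disease is already covered. Toxicity is assessed before each dose. Vital signs, weight and a symptom-directed examination fall on Day 21 and Day 42. Appendix I calls for thyroid tests when unexplained symptoms appear, and an investigator may order a TSH at any time. Criterion 7 accepts a TSH below 13 at entry, so the protocol tolerates mild elevation in patients going on to both drug and surgery. For the mildest silent changes, Table 4 continues the drug. All of this stands, and it confines the gap to symptom-free changes in completers. It does not close the gap, because each of these safeguards depends on symptoms or discretion.

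Adding a TSH before dosing also brings it under the rule that laboratory values must be acceptable, which could invite discretionary holds in a short course before curative surgery. That is a real cost, and the fix has to address it.

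A reader might infer that the trial will under-count thyroid toxicity. The documents give no rate or onset time for silent thyroid events, and Section 4.3 exempts clinically insignificant laboratory results from recording, so no under-count can be claimed. A reader might also infer that the calendar breaks the rule on acceptable laboratory values before dosing. That rule names no test, so there is no contradiction.

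**Conclusion.** The point holds as a minor, inexpensive improvement. Completers have no scheduled TSH between dose 1 and surgery. The first post-dose value comes 57 to 87 days after dose 1, and the value available at surgery is 52 to 100 days old (up to 114). These ranges assume an on-schedule completer with no held dose, dose 1 on Day 1, and surgery counted from dose 3. Held doses or the end-of-cycle reading lengthen them.

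The gap does not extend to patients who stop early, who have a TSH within 30 days of their last dose. Nor does it reach the primary analysis: feasibility turns on completing three cycles and resection, and no TSH result enters that definition. The benefit of closing the gap cannot be quantified from the documents.

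**What to change.** In the Section 9 calendar, mark TSH at Day 21 and Day 42 on the existing hematology and chemistry draws, and keep the Screening and Follow-Up marks. State that results are managed under the existing Table 4, so that a mild symptom-free change does not by itself delay a dose. Eligibility and Table 4 stay as they are.

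The cost is one calendar row and 2 × 20 = 40 assays, with no added visit or needle. Some additional thyroid adverse events will be recorded where judged clinically significant, and some discretionary holds are possible. The Day 42 sample precedes dose 3, so the interval from dose 3 to surgery still has no scheduled TSH. Covering it would need a third assay per patient (3 × 20 = 60 in all) at a visit with no safety-laboratory draw on the calendar. That is not proposed here.
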